At the end of their students' attachments, their GP teachers will complete a SurveyMonkey questionnaire that asks them to complete the PPOS D12 form. Consent to use these data for research will also be requested.

Each of these questionnaires will ask for the participant's name, so that pre-intervention, post-intervention, and GP's data can be linked and compared.

Outcome measures

The primary outcome measure will be the change in students' PPOS-D12 scores from baseline (at the start of the academic year) to the end of their year-long primary care attachment.

Secondary outcomes will be the effect of students' gender, previous experience and prior exposure to chronic illness in the participant or her/his close relatives and friends on their PPOS-D12 scores

A nested study will measure the strength of association between the GP teachers' own levels of patient/doctor-centredness and changes in their students' levels over the year.

Development of the intervention

Following a literature review and discussion, RF, [name] and MH developed a patient interview pro-forma which was designed to identify patients' views on their illnesses, how it affects their lives in physical, psychological and social terms, and how their relationships with their GPs impacts on their lives. The sections of the interview pro-forma map across to Mead and Bower's conceptual framework of patient-centredness given above [22].

Six medical students who had been visiting their GP teachers for eight half-days per year since their first year of study agreed to pilot the intervention in November 2017. The GP teachers were asked to select a patient with a chronic illness for their students, and to organise 2.5-hour interviews, half of the students at the patients' home and in the other half in the teaching practices. Students were asked to use the questionnaire pro-forma. In addition, the students each had a 30-minute interview with a practice nurse to assess their perceptions of the effect of the illnesses on their patients, and finally a one-hour discussion with their GP teacher to reflect on their encounters with the patients, discuss their findings, and talk about any difficulties that may have arisen.

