- Students. In a tailored informed consent procedure, students will be given a 'high-level description' of the study objectives with only superficial information on the study interventions, as accepted by ethics committees in similar studies. They will be informed that they are randomised to one of two study groups, without revealing that one is an intervention and the other is a sham comparator. The aim of this is to minimise performance and other reporting biases.
- GP teachers. A similar approach will be taken with information for the GP teachers, so that they also have only a 'high-level' description of the study objectives.

Statistical analysis

Descriptive statistics will be used to describe the relationships between student demographics and PPOS scores. Mean pre- and post-test PPOS scores will be compared using paired *t* tests. Differences between PPOS scores in the intervention and control groups will be examined with unpaired *t* tests. For the nested study, GPs' PPOS scores and changes in their students' PPOS scores will be compared using paired *t* tests.

The sample size calculation for the primary outcome was based on reported mean reduction of 0.11 in the PPOS score over one year in a group without any intervention [20], and a mean increase of 0.05 in the intervention group. We therefore assumed a mean difference 0.16, with a standard deviation of 0.42. The study was designed with a 5% level of significance and a 90% power to reject the null hypothesis of equivalence between the two groups. To achieve this objective, 220 students would be required (110 for each group). Assuming a 20% drop-out, we therefore aimed to enrol a total of 275 students.

Discussion

This research will consider the effect of an in-depth, structured interview with a patient with a chronic illness on changes in first-year medical students' levels of patient-centredness. There is existing evidence that medical students' levels of patient-centredness reduce over their student years, and this study will contribute to an understanding of how this reduction can be minimised or reversed.

Strengths

To our knowledge, this is the first randomised controlled trial that has been designed to study the effect of an intervention on medical students' levels of patient-centredness. The intervention materials were carefully developed and piloted by GP teachers and medical students, and therefore grounded in their clinical and educational experience.

Limitations

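### The plan meets its expected 20% loss only by enrolling more students; unadjusted t tests would be biased if end-survey loss depended on baseline score differently by arm, and adjusting for baseline removes that risk and adds power

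*Combined protocol and SAP*

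**What the plan says.** Under Outcome measures, the primary outcome is the "change in students' PPOS-D12 scores from baseline (at the start of the academic year) to the end of their year-long primary care attachment".

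Under Statistical analysis, two tests bear on the students' scores: "Mean pre- and post-test PPOS scores will be compared using paired" *t* tests, and "Differences between PPOS scores in the intervention and control groups will be examined with unpaired" *t* tests. The section does not say whether the unpaired test is on change or on the end score.

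The sample size text in the same section sets the design values: "We therefore assumed a mean difference 0.16, with a standard deviation of 0.42". It arrives at 110 analysed students per group and then inflates: "Assuming a 20% drop-out, we therefore aimed to enrol a total of 275 students".

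That inflation is the whole provision for loss. The document states no analysis population, no rule that students are analysed in their allocated arm, no missing-data method, no baseline adjustment and no sensitivity analysis. The Limitations section mentions low consent but not attrition.

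**The concern.** Enrolling 275 instead of 220 restores the number of students analysed. It does not ensure that those who remain in the two arms are still comparable.

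A change score needs both forms, linked by name, so a student who returns only the first form drops out of the primary comparison. Change is usually related to the starting score: students who start low tend to rise, and students who start high tend to fall. If the students who fail to return the end form differ in baseline attitude between the arms, the remaining groups have different expected change even when the interview has no effect. That error is in the point estimate, so a larger sample does not shrink it.

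The baseline score that would correct for this is already collected from students before the interventions, but the between-arm test does not use it. Leaving it out also gives up precision, whatever the loss pattern turns out to be.

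**Working it through.** **Inputs from the document.** Difference 0.16, SD 0.42, 110 per group and 20% loss (Statistical analysis). SD 0.48 at the start of the year, 0.51 at the end and 0.42 for change, from the cited one-year cohort of residents (Background); the 0.42 is also the SD used for sample size.

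**The plan's own figures.** 220/(1 - 0.20) = 275, so the inflation step reproduces. The power does not. With a two-sided 5% test, SE = 0.42 × √(2/110) = 0.0566, and 0.16/0.0566 - 1.96 = 0.865, which is about 81% power and not 90%. That is a separate matter, but it makes any gain in precision more useful.

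**Correlation and slope.**
- r = (0.48² + 0.51² - 0.42²)/(2 × 0.48 × 0.51) = 0.3141/0.4896 = 0.642
- slope of end score on baseline = 0.642 × 0.51/0.48 = 0.682
- slope of change on baseline = 0.682 - 1 = -0.318

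**Bias formula.** Bias of the change-score comparison = -0.318 × 0.48 × g, where g is the gap between arms, in baseline SDs, in the mean baseline of the students who remain. For an end-score comparison, replace -0.318 by +0.682.

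**Loss scenarios (assumed).** 20% is lost in each arm. Loss is unrelated to baseline in the reading arm. In the interview arm the log-odds of loss are linear in baseline, which is taken as normal.

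| Odds of loss per SD lower baseline, interview arm | g | Bias, change | Bias, end score |
|---|---|---|---|
| 1 (unrelated), or the same relation in both arms | 0 | 0 | 0 |
| 1.65 | 0.096 | -0.015 | +0.031 |
| 2 | 0.129 | -0.020 | +0.042 |
| 2.7 | 0.172 | -0.026 | +0.056 |
| Limiting case: lowest 20% all lost | 0.350 | -0.053 | +0.115 |

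Swapping the arms reverses every sign. In a simulation of 275 students under the two-fold scenario, the change-score t test had a type I error of 7.1% and power of 70%, against 80.7% power when loss was unrelated to baseline.

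**Sensitivity to the slope.** The slope is borrowed from residents. At -0.2 the 1.65- and 2.7-fold biases become -0.2 × 0.48 × 0.096 = -0.009 and -0.2 × 0.48 × 0.172 = -0.017. At -0.5 they become -0.023 and -0.041.

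**Effect of conditioning on baseline.** In the same simulations, ANCOVA on the students with both forms estimated 0.159 to 0.161 for a true 0.16. This is expected, since loss was simulated to depend only on arm and baseline. The residual SD is 0.51 × √(1 - 0.642²) = 0.391. At 110 per group, SE = 0.391 × √(2/110) = 0.0527, and 0.16/0.0527 - 1.96 ≈ 1.07, or about 86% power.

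**The case against.** The strongest reply is that nothing in the document shows the loss pattern this needs. Study design has all students complete both forms. Data collection has the end form ask whether the student had the interview, the reading or neither, and why. Skipping the session is therefore not the same as missing the outcome: the outcome is sought from students who skipped. Both arms use the same last half-day, and students are not told which activity is the comparator. No figure is given on who fails to respond.

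This stands, and it makes the bias conditional. Seeking the form does not guarantee its return, however, and the plan itself expects 20% loss.

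Three stronger readings are tempting and are not supported.
- **That the planned analysis is biased as it stands.** It is biased only if survey loss depends on baseline differently by arm. The 2.7-fold scenario is a strong one: it loses about 41% of the lowest baseline quarter of the interview arm and 6% of the highest.
- **That the interview session is so much longer that it must drive students out.** A four-hour total can be formed only by adding the pilot's timings (2.5 hours, 30 minutes and 1 hour). Half of those pilot interviews were in the practice, and the organisation was then revised.
- **That the plan leans towards a false positive.** The declared primary outcome is change, and there the scenarios above pull towards the null. The upward bias belongs to an end-score test, which the loose wording of Statistical analysis permits but Outcome measures does not make primary. That test would also need only the end form.

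**Conclusion.** The point holds in conditional form. The plan expects to lose a fifth of its students, provides only for the lost numbers, and leaves the baseline score out of the comparison of arms. If end-survey loss relates to baseline differently by arm, the change-score estimate shifts by about -0.015 to -0.026 in the one-arm scenarios, which is 9% to 16% of the planned 0.16. The limiting case of -0.053 is a third of it.

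The size rests on assumed odds of loss and on SDs from residents, not first-year students; the Limitations section already warns that such data may not carry over. The direction depends on which arm loses which students.

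The case for change does not depend on the bias occurring. With the cited SDs, adjustment gains about five points of power at 110 per group even when loss is unrelated to baseline.

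**What to change.** - **Primary analysis.** Replace the unpaired t test with ANCOVA of the end PPOS-D12 score (or, equivalently for the arm effect, of change) on arm and baseline PPOS-D12, with students in their allocated arm whatever activity they report. State the analysis set.
- **Alternative.** A longitudinal model with a common baseline mean could also include students with only the first form, if their consent covers it. Data collection mentions the data-use request only with the end form, and Ethics approval and consent to participate does not say which survey carries the agreement button. This should be clarified first.
- **Reporting.** Tabulate loss by arm and by baseline score.
- **Optional sensitivity analysis.** Conditioning on baseline does not deal with loss that depends on the unobserved end score. One delta-adjusted analysis would: lower the imputed outcomes of lost interview-arm students by a range of deltas and report where the 95% interval reaches zero. For an observed 0.16 under the adjusted model, the half-width is about 1.96 × 0.0527 = 0.103, so the tipping delta is roughly (0.16 - 0.103)/0.20 = 0.28.

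The ANCOVA needs revised wording and a few lines of code, with no new data. The cost is slightly more complex reporting than a t test.

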Appendix 1. PPOS-D12 English translation

Possible Likert-scale responses: 'I completely agree'; 'I agree'; 'I agree slightly'; 'I disagree slightly'; 'I disagree'; 'I completely disagree'.

1. Although treating patients today is not so personal anymore, it is ultimately a small price for medical advancement.
2. The most important part of the normal visit is the physical examination.
3. Patients should rely on the knowledge of their doctors and not try to inform themselves about their condition.
4. When doctors ask a lot of questions about a patient's personal situation, they are too involved in private matters.
5. When doctors are really good at diagnosis and therapy, their treatment of patients is not so important.
6. Many patients keep asking questions without really learning anything new.
7. Patients tend to want to hear that everything is good, rather than real information about their health.
8. When doctors first try to be open and make a warm-hearted impression, they will not be so terribly successful.
9. If patients disagree with their doctors, it shows that they disrespect their doctors and do not trust them.
10. The patient must always be aware that the doctor is responsible.
11. It is not so important to know the cultural background of a patient and his life situation in order to treat his illness.
12. When patients get their own medical information, it often confuses them more than it helps them.
